### 9.5.6 Abuse or Diversion of Study Drug

Not applicable

## 9.6 Data Quality Assurance

This study will be organized, performed, and reported in compliance with the protocol, SOPs, working practice documents, and applicable regulations and guidelines. Site audits will be made periodically by the sponsor's or the CRO's qualified compliance auditing team, which is an independent function from the study team responsible for conduct of the study.

### 9.6.1 Data Collection

Data required by the protocol will be collected on the CRFs and entered into a validated data management system that is compliant with all regulatory requirements. As defined by ICH guidelines, the CRF is a printed, optical, or electronic document designed to record all of the protocol-required information to be reported to the sponsor on each study subject.

Data collection on the CRF must follow the instructions described in the CRF Completion Guidelines. The investigator has ultimate responsibility for the collection and reporting of all clinical data entered on the CRF. The investigator or designee as identified on Form FDA 1572 must sign the completed CRF to attest to its accuracy, authenticity, and completeness.

Completed, original CRFs are the sole property of Eisai and should not be made available in any form to third parties without written permission from Eisai, except for authorized representatives of Eisai or appropriate regulatory authorities.

## 9.6.2 Clinical Data Management

All software applications used in the collection of data will be properly validated following standard computer system validation that is compliant with all regulatory requirements. All data, both CRF and external data (eg, laboratory data), will be entered into a clinical system.

## 9.7 Statistical Methods

All statistical analyses will be performed by the sponsor or designee after the study is completed and the database is locked and released. Statistical analyses will be performed using SAS software or other validated statistical software as required. Details of the statistical analyses will be included in a separate statistical analysis plan (SAP).

### 9.7.1 Statistical and Analytical Plans

The statistical analyses of study data are described in this section. Further details of the analytical plan will be provided in the SAP, which will be finalized before database lock.

#### 9.7.1.1 Study Endpoints

##### 9.7.1.1.1 PRIMARY ENDPOINT

The primary endpoint is the safety and tolerability of subsequent systemic TPC following the first-line lenvatinib treatment in uHCC subjects, and will be analyzed by summarizing the incidence of treatment-emergent adverse events (TEAEs) and SAEs.

##### 9.7.1.1.2 SECONDARY ENDPOINTS

- Overall survival (OS), measured from the date of first dose of study treatment until date of death from any cause. Subjects who are lost to follow-up will be censored at the last date the subject was known to be alive, and subjects who remain alive will be censored at the time of data cutoff.
- Progression-free survival (PFS), defined as the time from the date of first dose of first-line lenvatinib treatment to the date of first documentation of disease progression, or date of death, during the subsequent systemic TPC, whichever occurs first.
- Time to progression (TTP), defined as the time from the date of first dose of first-line lenvatinib treatment to the date of first documentation of disease progression during subsequent systemic TPC.

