### **Analysis Sets**

**Safety Analysis Set (Full Analysis Set)** is the group of subjects who received at least 1 dose of the lenvatinib treatment. This will be the analysis set for all safety and efficacy evaluations.

**The Pharmacodynamic Analysis Set** is all the subjects who have received at least 1 dose of lenvatinib and had sufficient pharmacodynamic data to derive at least 1 pharmacodynamic measurement and with documented dosing history.

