#### 9.1.2.2 Subsequent Treatment Period (TPC Period, Treatment Period 2)

The subsequent TPC period will begin upon the completion of the lenvatinib Off-Treatment Visit in first-line treatment of lenvatinib. Subjects will be treated with commercially available systemic TPC for uHCC. The first treatment of a single agent or combination of multiple drugs after lenvatinib treatment will be considered as the subsequent TPC. Locoregional therapies (ie, chemoembolization/radioembolization, etc) procedures will not

be considered as a second line treatment following lenvatinib. If the investigator deems a subject inappropriate for commercially available systemic TPC as the subsequent treatment following lenvatinib, subjects will be followed in the survival Follow-Up period. All treatment following lenvatinib will be captured in the case report form. Data will be collected from the start of TPC, then at intervals as indicated in Schedule of Procedures/Assessments ([Table 3](#)).

Subjects starting subsequent TPC  $\geq$ 8 weeks after lenvatinib off-treatment visit may be considered after discussion with sponsor.

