#### 9.7.1.2 Definitions of Analysis Sets

The **Safety Analysis Set (Full Analysis Set)** is the group of subjects who received at least 1 dose of study drug. This will be the analysis set for all safety and efficacy evaluations.

The **Pharmacodynamic Analysis Set** is all the subjects who have received at least 1 dose of lenvatinib and had sufficient pharmacodynamic data to derive at least 1 pharmacodynamic measurement and with documented dosing history.

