#### 9.7.1.6 Efficacy Analyses

Efficacy analyses will be performed based on the Safety Analysis Set.

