## **TPP**

TPP (based on the tumor response evaluation as determined by investigator assessment according to mRECIST) will be evaluated using same procedure as used for PFS.

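### PFS counts deaths only during TPC but is analysed in everyone dosed with lenvatinib, so subjects who never start TPC cannot have an event and full-set PFS is biased upward

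*Combined protocol and SAP*

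**What the plan says.** Synopsis (Secondary Endpoints) and Section 9.7.1.1.2 run PFS from the first lenvatinib dose to first documented progression "or date of death, during the subsequent systemic TPC, whichever occurs first". TTP in the same lists has the same start and is likewise limited to progression during TPC. Section 8.2 describes the objective as PFS and TTP of the TPC, timed from lenvatinib start.

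The analysis set is wider than that window. In the synopsis, the Safety (Full) Analysis Set "is the group of subjects who received at least 1 dose of the lenvatinib treatment". Section 9.7.1.2 adds: "This will be the analysis set for all safety and efficacy evaluations". Section 9.7.1.6 repeats it: "Efficacy analyses will be performed based on the Safety Analysis Set". No TPC-treated efficacy set is defined.

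Non-starters are foreseen. Section 9.1.2.2 has a clause beginning "If the investigator deems a subject inappropriate for commercially available systemic TPC" that sends such subjects to survival follow-up. Section 9.1.2.3 and Table 3 footnote w set that follow-up at every 12 weeks, so their deaths are recorded.

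OS carries a censoring rule ("Subjects who are lost to follow-up will be censored at the last date the subject was known to be alive"). PFS and TTP carry none in the text available, and Section 9.7.1.6 says only that TTP "will be evaluated using same procedure as used for PFS". Section 9.7.1 defers detail: "Further details of the analytical plan will be provided in the SAP, which will be finalized before database lock".

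**The concern.** The clock and the set cover the whole treatment sequence, while the event window covers only its second part. A subject who stops lenvatinib, never receives TPC and dies contributes time at risk to the PFS curve but can never contribute a failure. The reported median would therefore look better when fewer subjects reach TPC.

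PFS and TTP are the protocol's only progression-based read-outs for treatment after lenvatinib. A SAP that follows the endpoint wording faithfully would inherit the problem.

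**Working it through.** **The plan's own figure.** The documents state no number for PFS or TTP. The only sizing figure is Table 4 (Section 9.7.2), the half width 1.96 × √(0.75 × 0.25 / n). For n = 100, 90, 80, 70, 60 and 50 it gives 8.49, 8.95, 9.49, 10.14, 10.96 and 12.00%, against 8.5, 8.9, 9.5, 10.1, 11 and 12% stated. It reproduces. It also shows the planned range of TPC uptake: 50% to 100% of 100 subjects.

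**Subjects who cannot have an event.** 100 × (1 − 0.50) = 50 at the planning floor.

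**Direction.** If a non-starter's death is censored on the death date instead of counted, a factor below 1 drops out of the Kaplan-Meier product and later risk sets are unchanged. The curve can only rise or stay the same, and this needs no assumptions. If non-starters are instead censored earlier, at lenvatinib stop, the direction is not guaranteed by algebra, but it was upward in every scenario run.

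**Size (illustration).**

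- From the documents: lenvatinib duration 6 to 8 months (Synopsis, Duration of Treatment), used as an exponential mean of 7; uptake *u* from 50% (Section 9.7.2).
- Assumed: 1-month gap before TPC; exponential time from TPC start to progression or death with median 3, 4 or 6 months; exponential survival after lenvatinib without TPC with median 3 or 5 months; non-starters censored at lenvatinib stop or at death.

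Formulas, with S_c the survival function of the non-starters' censoring time:

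- As written: hazard h(t) = u·f_TPC(t) / [u·S_TPC(t) + (1 − u)·S_c(t)], and PFS(t) = exp(−∫h).
- All deaths counted: PFS(t) = u·S_TPC(t) + (1 − u)·S_death(t).

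Medians in months at u = 50%:

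| TPC PFS median | No-TPC survival median | As written, censored at lenvatinib stop | As written, censored at death | All deaths counted |
|---|---|---|---|---|
| 3 | 3 | 13.4 | 15.6 | 9.9 |
| 3 | 5 | 13.4 | 17.0 | 11.1 |
| 4 | 3 | 14.6 | 16.9 | 10.5 |
| 4 | 5 | 14.6 | 18.3 | 11.8 |
| 6 | 3 | 17.0 | 19.2 | 11.5 |
| 6 | 5 | 17.0 | 20.8 | 13.0 |

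The smallest overstatement is 13.4 − 11.1 = 2.3 and the largest is 20.8 − 13.0 = 7.8 months. At 70% uptake the range is about 1 to 4 months, and at 90% it is 0.2 to 1.2. Twelve-month PFS at 50% uptake is 56 to 76% as written, against 39 to 54% with all deaths counted.

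**Sensitivity.** With lenvatinib mean 6 to 8 and gap 0.5 to 3 months, the overstatement is 1.8 to 8.3 months at 50% uptake and 0.2 to 1.3 at 90%. If 6 to 8 months is read as a median, it is 3.1 to 10.1 and 0.3 to 1.5.

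**Dependence on the censoring rule.** A separate simulation used lenvatinib median 7 months, gap 1, both later medians 3, a 30-month cutoff and 50% uptake. The as-written median was 17.4 months with non-starters censored at lenvatinib stop, 19.8 with censoring at death, and not reached if they are held to data cutoff. With all deaths counted it was 12.2.

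**The case against.** **The target is PFS of TPC, so all-death PFS in everyone dosed is the wrong yardstick.** This stands in part. The bias is relative to a PFS that counts all deaths. Table 4 already uses TPC recipients as denominator for a TPC question, and a SAP could do the same for PFS. But that departs from Sections 9.7.1.2 and 9.7.1.6. With the lenvatinib clock kept, it also builds in an event-free lead-in, since recipients must come through lenvatinib to be included.

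**The SAP will deal with it.** A reader might infer that the plan has no PFS or TTP censoring rule at all. The documents do not support that, because Section 9.7.1 defers detail to a separate SAP whose text was not available here. The event definition, however, sits in the protocol, and a censoring rule alone leaves excluded deaths excluded.

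**The window may modify death only.** The parallel TTP definition and the objective in Section 8.2 point to both event types. On the narrower reading, progression on lenvatinib would count, but a death without TPC and without earlier progression would still be lost.

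**The size is assumed.** This stands. Only the lenvatinib duration and the uptake floor come from the documents.

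**OS by TPC subgroup.** A reader might also infer that this analysis lacks a time origin. It does not: Section 9.7.1.1.2 measures OS from first dose of study treatment and defines no different origin for subgroups.

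**Conclusion.** The point holds. The PFS event window and the analysis set are not reconciled, and followed literally they bias full-set PFS upward relative to a PFS that counts all deaths. TTP has the same mismatch, since a non-starter can never have a TTP event either. The direction is firm. The size is illustrative: about 2 to 8 months on the median at 50% uptake, falling to about 0.2 to 1.2 months at 90%, under the exponential model and inputs listed above.

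It would go too far to say that the trial's conclusions are compromised. PFS and TTP are secondary and descriptive, so no hypothesis test, the primary safety endpoint and the sample size are all unaffected. The harm is a misleading estimate, which should be fixed before the SAP is finalized.

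**What to change.** 1. In the synopsis and Section 9.7.1.1.2, keep the full set and the lenvatinib-start clock. Define the event as first documented progression on TPC or death from any cause at any time, and label it 'progression on TPC or death'. Censor event-free TPC starters at their last evaluable tumor assessment on TPC, and event-free non-starters at the date last known alive.
2. Add PFS and TTP from first TPC dose in TPC-treated subjects, using the new tumor baseline that Section 9.5.1.3.1 already requires. This is the direct read-out for the objective in Section 8.2. It is needed beside item 1, because item 1 ignores progression on lenvatinib in non-starters and so mixes two kinds of event.

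**Cost.** Wording in two places, a line in Section 9.7.1.6, and the SAP. Survival status, TPC dates and TPC scans are already collected. Reported medians will be shorter, and two clocks must be labelled.

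**What remains.** The repaired median can still move slightly with uptake: with TPC PFS median 3 and no-TPC survival median 5 months it is 10.4 at 100%, 10.8 at 70% and 11.1 at 50%. A small upward bias also remains for subjects who stop TPC without progression and die later, because scans are collected only until the end of TPC (Table 3, footnote aa). In simulation, with TPC stopped without progression at up to half the progression hazard, this was about 0.5 month at 50% uptake and about 1 month at 90%.

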##### 9.7.1.1.3 EXPLORATORY ENDPOINT

Patient-reported outcome (PRO) results from a well-defined PRO instrument (PRO-CTCAE) will be determined by scores in the subsequent TPC period.

#### 9.7.1.2 Definitions of Analysis Sets

The **Safety Analysis Set (Full Analysis Set)** is the group of subjects who received at least 1 dose of study drug. This will be the analysis set for all safety and efficacy evaluations.

The **Pharmacodynamic Analysis Set** is all the subjects who have received at least 1 dose of lenvatinib and had sufficient pharmacodynamic data to derive at least 1 pharmacodynamic measurement and with documented dosing history.

#### 9.7.1.3 Subject Disposition

The number (percentage) of subjects who completed the study treatment/study and discontinued from the study treatment/study and reasons for discontinuation will be provided.

#### 9.7.1.4 Demographic and Other Baseline Characteristics

Demographic and other baseline characteristics for the Full Analysis Set will be summarized using descriptive statistics. Continuous demographic and baseline variables include age, BW, and height; categorical variables include sex, age group, BW group, race, region, macroscopic portal vein invasion and/or extra hepatic spread, ECOG-PS, NYHA cardiac disease classification, BCLC staging, and Child-Pugh score.

#### 9.7.1.5 Prior and Concomitant Therapy

All investigator terms (verbatim terms) for medications recorded in the CRF will be coded to an 11-digit code using the World Health Organization Drug Dictionary (WHO DD). The number (percentage) of subjects who took prior and concomitant medications will be summarized, using Anatomical Therapeutic Chemical (ATC) class and WHO DD preferred term. Prior medications will be defined as medications that stopped before the first dose of study drug. Concomitant medications will be defined as medications that (1) started before the first dose of study drug and were continuing at the time of the first dose of study drug, or (2) started on or after the date of the first dose of study drug up to 28 days after last dose of lenvatinib treatment if subjects do not enter TPC period, or for 8 weeks after the start of TPC period or up to 28 days after last dose of TPC if subject does not stay in the TPC period for the 8 weeks of safety monitoring. All medications will be presented in subject data listings. All anticancer therapy will be recorded until time of death or termination of survival follow-up.

#### 9.7.1.6 Efficacy Analyses

Efficacy analyses will be performed based on the Safety Analysis Set.

### OS

The median OS and the cumulative probability of OS at selected time points will be calculated and presented with 2-sided 95% CIs. The selected time points will depend on the

OS times that are observed during the study and will be specified in the SAP. Kaplan-Meier (KM) estimates of OS will be plotted over time.

## **PFS**

Median PFS time and the cumulative probability of PFS at selected time points will be calculated, and presented with corresponding 2-sided 95% CIs. The selected time points will depend on the PFS times that are observed during the study and will be specified in the SAP. KM estimates of PFS will be plotted over time.

## **TPP**

TPP (based on the tumor response evaluation as determined by investigator assessment according to mRECIST) will be evaluated using same procedure as used for PFS.

### **9.7.1.7 Pharmacokinetic, Pharmacodynamic, Pharmacogenomic, and Other Biomarker Analyses**

#### **9.7.1.7.1 PHARMACOKINETIC ANALYSES**

Not applicable

#### **9.7.1.7.2 PHARMACODYNAMIC, PHARMACOGENOMIC, AND OTHER BIOMARKER ANALYSES**

The effect of study treatment on soluble, tissue, genetic and/or other relevant biomarkers will be summarized using descriptive statistics using the Pharmacodynamic Analysis Set and correlated with clinical outcomes-related endpoints for safety and/or efficacy as appropriate. Details will be included in a separate analysis plan.

### **9.7.1.8 Safety Analyses**

All safety analyses based on Safety Analysis Set will be performed for each treatment period. Safety data will be summarized on an “as treated” basis. The incidence of TEAEs and SAEs will be summarized. Laboratory test results, vital signs and their changes from baseline, and 12-lead ECG and echocardiogram results including LVEF, will be summarized using descriptive statistics. Abnormal values will be flagged.

#### **9.7.1.8.1 EXTENT OF EXPOSURE**

The number of cycles/days on treatment, quantity of study drug administered, and the number of subjects requiring dose reductions, treatment interruption, and treatment discontinuation due to AEs will be summarized.

Additionally, the following data will be summarized: percentage of subjects that receive TPC, average dose intensity and relative dose intensity of lenvatinib treatment and TPC, and feasibility rate (defined as the percentages of subjects completing the first 2, 4, and 6 cycles of lenvatinib treatment without requiring dose reduction due to AE).

#### 9.7.1.8.2 ADVERSE EVENTS

Adverse Events will be graded using CTCAE v4.03. The AE verbatim descriptions (investigator terms from the CRF) will be classified into standardized medical terminology using the Medical Dictionary for Regulatory Activities (MedDRA). Adverse events will be coded to the MedDRA lower level term (LLT) closest to the verbatim term. The linked MedDRA preferred term (PT) and primary system organ class (SOC) are also captured in the database.

A TEAE is defined as an AE that emerges during treatment, having been absent at pretreatment (baseline) or

- Reemerges during treatment, having been present at pretreatment (baseline) but stopped before treatment, or
- Worsens in severity during treatment relative to the pretreatment state, when the AE is continuous.

TEAE will be defined and summarized for each treatment period separately.

Only those AEs that are treatment emergent will be included in summary tables. All AEs, treatment emergent or otherwise, will be presented in subject data listings.

The incidence of TEAEs will be reported as the number (percentage) of subjects with TEAEs by SOC and PT. A subject will be counted only once within an SOC and PT, even if the subject experienced more than 1 TEAE within a specific SOC and PT. The number (percentage) of subjects with TEAEs will also be summarized by highest CTCAE grade. The number (percentage) of subjects with TEAEs will also be summarized by relationship to study drug (probably related, possibly related, and not related).

The number (percentage) of subjects with treatment-related TEAEs will be summarized by SOC and PT. Treatment-related TEAEs include those events considered by the investigator to be related to study treatment.

The number (percentage) of subjects with treatment-emergent SAEs will be summarized by MedDRA SOC and PT. A subject data listing of all SAEs will be provided.

The number (percentage) of subjects with TEAEs leading to discontinuation from study drug or leading to study drug dose changes will be summarized by MedDRA SOC and PT. A subject data listing of all AEs leading to discontinuation from study drug or leading to study drug dose changes will be provided.

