#### 9.4.2.3 Labeling for Study Drug

Lenvatinib will be labeled in accordance with text that is in full regulatory compliance with each participating country and is translated into the required language for each of those countries.

Medications chosen by investigator for subsequent treatment will not be provided by the sponsor.

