#### 9.4.2.4 Storage Conditions

The sponsor will prepare the “Procedures for Handling Investigational Drug” which will be provided to the investigator, head of medical institution (as required by regional authority), or designated study drug manager before the investigational drug is delivered. The investigational drug will be stored in accordance with the “Procedures for Handling Investigational Drug.”

Lenvatinib will be stored in accordance with the labeled storage conditions. The expiry date for lenvatinib will be established based on the date that manufacturing/packing is completed or will be based on formulation testing, and will therefore be described in the “Procedures for Handling Investigational Drug.”

Study drug to be used in Period 2 will be stored as described in the locally approved product label or in the applicable Summary of Product Characteristics.

Temperature monitoring is required at the storage location to ensure that the study drug is maintained within an established temperature range. The investigator or designee (or if regionally required, the head of the medical institution) is responsible for ensuring that the temperature is monitored throughout the total duration of the study and that records are maintained. The temperature should be monitored continuously by using either an in-house validated data acquisition system, a mechanical recording device, such as a calibrated chart recorder, or by manual means, such that minimum and maximum thermometric values over a specific time period can be recorded and retrieved as required.

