### **Assessing Relationship to Study Treatment**

Items to be considered when assessing the relationship of an AE to the study treatment are:

- Temporal relationship of the onset of the event to the initiation of the study treatment
- The course of the event, especially the effect of discontinuation of study treatment or reintroduction of study treatment, as applicable
- Whether the event is known to be associated with the study treatment or with other similar treatments

- The presence of risk factors in the study subject known to increase the occurrence of the event
- The presence of nonstudy, treatment-related factors that are known to be associated with the occurrence of the event

*Classification of Causality*

The relationship of each AE to the study drug will be recorded on the CRF in response to the following question:

Is there a reasonable possibility that the study drug caused the AE?

Yes (related) A causal relationship between the study drug and the AE is a reasonable possibility.

No (not related) A causal relationship between the study drug and the AE is not a reasonable possibility.

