## **11.8 Handling of Study Drug**

All study drug will be supplied to the PI (or a designated pharmacist) by the sponsor. Drug supplies must be kept in an appropriate secure area (eg, locked cabinet) and stored according to the conditions specified on the drug labels. The investigator (or a designated pharmacist) must maintain an accurate record of the shipment and dispensing, returns and destruction of the study drug in a drug accountability ledger, a copy of which must be given to the sponsor at the end of the study. An accurate record of the date and amount of study drug dispensed to each subject must be available for inspection at any time. The CRA will visit the site and review these documents along with all other study conduct documents at appropriate intervals once study drug has been received by the site.

All drug supplies are to be used only for this study and not for any other purpose. The investigator (or site personnel) must not destroy any drug labels or any partly used or unused drug supply before approval to do so by the sponsor. At the conclusion of the study and as appropriate during the study, the investigator (or a designated pharmacist) will return all used and unused drug containers, drug labels, and a copy of the completed drug disposition form

to the sponsor's CRA (or designated contractor) or, when approval is given by the sponsor, will destroy supplies and containers at the site.

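### AE causality is collected as Yes/No against an undefined study drug but is to be tabulated in three levels, and the Period 2 related-event table will not clearly show relationship to TPC

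*Combined protocol and SAP*

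**What the plan says.** On collection, Section 9.5.1.5.1 (Assessing Relationship to Study Treatment) states: "The relationship of each AE to the study drug will be recorded on the CRF in response to the following question". The question is "Is there a reasonable possibility that the study drug caused the AE", and two answers are offered: "Yes (related) A causal relationship between the study drug and the AE is a reasonable possibility", or "No (not related) A causal relationship between the study drug and the AE is not a reasonable possibility".

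On analysis, Section 9.7.1.8.2 says that TEAEs will be "summarized by relationship to study drug (probably related, possibly related, and not related". The same section defines and summarizes TEAEs for each treatment period separately. It also plans a table of treatment-related TEAEs, meaning events that the investigator considers related to study treatment.

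On what *study drug* is, the protocol points two ways. Section 11.8 says: "All study drug will be supplied to the PI (or a designated pharmacist) by the sponsor". Section 9.4.2.3 says: "Medications chosen by investigator for subsequent treatment will not be provided by the sponsor", and Section 9.4.2 has TPC coming from the local pharmacy. Together these make study drug lenvatinib only. Section 9.4.2.4, however, says: "Study drug to be used in Period 2 will be stored as described in the locally approved product label", which extends the term to TPC. The list of abbreviations and definitions in Section 4 does not define it.

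**The concern.** There are two separate faults. The first is a plain mismatch between the response scale collected and the scale reported. The second concerns meaning: one causality item covers two periods with different drugs, and nothing says which drug the item asks about in Period 2.

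The second fault matters more. The primary objective is the safety and tolerability of systemic TPC after lenvatinib. Section 7.1 gives as the reason for the study that the safety of later medications was not captured in the earlier phase 3 trial of lenvatinib. A reader of the report will want to know which Period 2 events were judged related to TPC. If sites answer the question with different drugs in mind, the related / not related split in that period mixes different judgements. Attribution that was not recorded at the time is hard to recover later.

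**Working it through.** **Step 1. The plan's own design figure.** Table 4 in Section 9.7.2 gives 95% CI half widths for a Grade 3 or higher TEAE rate of 75%. The formula is 1.96 × √(0.75 × 0.25 / n):

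| n receiving TPC | Recomputed | Table 4 |
|---|---|---|
| 100 | 8.49% | 8.5% |
| 90 | 8.95% | 8.9% |
| 80 | 9.49% | 9.5% |
| 70 | 10.14% | 10.1% |
| 60 | 10.96% | 11% |
| 50 | 12.00% | 12% |

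All agree to rounding. The rate is for TEAEs of any cause, so neither the sample size nor its precision depends on the causality item.

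**Step 2. Levels collected against levels reported.** Two levels are collected and three are to be reported. No corresponds to not related. Yes corresponds to probable and possible taken together. If x subjects in a period have at least one Yes event, the number with a probably related event could be anything from 0 to x. The protocol describes no other item that grades likelihood. The three-level table therefore cannot be derived. A two-level table can be, and so can the separately planned treatment-related TEAE table, because its definition is already binary.

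**Step 3. What a Yes means in Period 2.**

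| Reading of *study drug* | Textual support | Meaning of Yes in Period 2 |
|---|---|---|
| Lenvatinib only | Section 11.8 read with 9.4.2 and 9.4.2.3; the Section 9.5.4.1 rule on reporting related SAEs without time limit names lenvatinib | Related to lenvatinib; relationship to TPC is not collected |
| Lenvatinib and TPC | Section 9.4.2.4 | Related to lenvatinib, TPC or both; which one is not recorded |
| The drug of the current period | Suggested by the study treatment row of Table 3 and by Section 9.4.3, but not stated for causality | Related to TPC |

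Only the third reading gives the table the study needs, and no section ties the causality question to it.

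**Step 4. Whether timing settles attribution.** Section 9.1.2.1 places the lenvatinib Off-Treatment Visit no later than 30 days after the last lenvatinib dose. Section 9.1.2.2 starts the TPC period when that visit is complete. No minimum interval between the two drugs is stated, and the Table 3 footnotes provide for a first TPC dose 7 days or less after the visit. The calendar alone does not attribute a new or worsened Period 2 event to one drug.

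**Step 5. Which events need an attribution.** Under Section 9.7.1.8.2 an event is treatment-emergent if it is new, if it re-emerges, or if it worsens. If pretreatment is read separately for each period, an event that began on lenvatinib and re-emerged or worsened on TPC is a Period 2 TEAE. A rule based only on onset after the first TPC dose could miss such events, although lenvatinib is an obvious candidate cause for them.

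**The case against.** The strongest reply is that little depends on this. Section 9.7.1.1.1 analyses the primary endpoint through TEAE and SAE incidence, with no reference to causality. Safety is summarized by period and as treated. The Table 3 footnotes call for a fresh TPC baseline for vital signs, physical examination, ECG and laboratory tests unless the Off-Treatment Visit was 7 days or less before the first TPC dose. An unchanged lenvatinib event would then not count as a Period 2 TEAE. The causality subsection is headed by study treatment rather than study drug and directs the investigator to the timing of onset after treatment began. Section 9.4.1.2 assumes that toxicity related to TPC can be recognized. Section 11.8 is drug-accountability text, not a definition for causality. Finally, the CRF, its completion guidelines and the separate SAP announced in Section 9.7 were not available and may settle the matter.

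Most of this stands as a limit on the consequence, and it rules out three stronger readings that a reader might infer:

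- *That the primary endpoint is compromised.* It is not, because it does not use causality.
- *That TPC toxicity cannot be separated from lenvatinib toxicity at all.* Period-specific TEAEs do separate them in time. What stays unclear is the attribution of new, re-emergent or worsened Period 2 events.
- *That a large share of Period 2 events is misattributed.* The documents give no duration of lenvatinib effect, no distribution of the gap between drugs and no event timing. Suppose, purely as an assumption, that the 28-day AE follow-up after lenvatinib marks the period of possible effect. The overlap with the 8-week (56-day) Period 2 window is then (28 − gap)/56, which is 50%, 25% and 0% for gaps of 0, 14 and 28 days. That is a share of calendar time, not of events, and the range includes zero.

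The reply does not remove the two-against-three mismatch, and it cites no sentence that fixes the meaning of study drug in Period 2.

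**Conclusion.** The point holds in limited form. The three-level causality table cannot be produced from the item described; this is certain on the text and applies to both periods. The Period 2 treatment-related TEAE table can be produced, but what it shows about TPC depends on an unstated reading of study drug. These are supporting tables. Event incidence, grade and seriousness are unaffected, and no number in the plan changes. The share of Period 2 events whose attribution would differ cannot be estimated from the documents.

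This rests on the protocol text alone. If the CRF already holds separate fields, or the separate SAP defines the drug assessed, what remains is a wording correction. It is worth making because TPC safety is the study's purpose and the remedy is cheap.

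**What to change.** 1. In Section 9.7.1.8.2, replace the three-level summary with related / not related, to match Section 9.5.1.5.1.
2. Define *study drug* and *study treatment* once, and use them consistently in the causality question and in the definition of treatment-related TEAEs.
3. For every AE that is treatment-emergent in Period 2, including AEs that began in Period 1 and re-emerged or worsened after the first TPC dose, record a Yes/No relationship to lenvatinib and, separately, a Yes/No relationship to TPC.
4. Define Period 2 treatment-related TEAEs as those related to TPC. Relationship to lenvatinib in Period 2 can be shown alongside.

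The cost is wording changes in Sections 9.5.1.5.1 and 9.7.1.8.2, plus one added Period 2 CRF field with its completion instruction, unless the CRF already has it. Treatment, visit schedule and sample size do not change.
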